Study Protocol

Title:

Effects of a Virtual Reality–Based Empathy Program on Empathy, Attitudes Toward Older Adults, and Empathic Behavior Among Nursing Assistants: A Cluster Randomized Controlled Trial

NCT No.: NCT07044492

Protocol Version: 4.0

Date: October 13, 2025

IRB Approval: Taipei Medical University Joint Institutional Review Board

IRB No.: N202203004

Principal Investigator: Principal Investigator (PI)

1. Background and Rationale

Empathy is a fundamental component of high-quality long-term care and is associated with improved interpersonal relationships, communication, and emotional well-being among older adults. Nursing assistants (NAs) provide the majority of direct daily care in long-term care institutions and play a critical role in empathic caregiving interactions. However, conventional empathy training approaches are often didactic in nature and may have limited impact on sustained empathic outcomes.

Virtual reality (VR)–based training provides immersive, first-person experiential learning that may enhance perspective-taking and emotional engagement. When combined with structured reflective debriefing, VR-based interventions have the potential to improve empathy-related outcomes, including empathic attitudes and observable empathic behaviors. This study evaluated the effectiveness of a VR-based empathy program with structured debriefing among nursing assistants working in long-term care settings, using a cluster randomized controlled trial design.

2. Objectives and Hypotheses

2.1 Primary Objective

To examine the effect of a virtual reality–based empathy training program on empathy level among nursing assistants.

2.2 Secondary Objectives

1. To evaluate changes in attitudes toward older adults.
2. To assess changes in empathic behavior over time.

2.3 Hypothesis

Nursing assistants in the intervention group will show significantly higher

empathic behavior scores over time compared with the control group.

3. Study Design

This study was a two-arm, parallel-group, cluster randomized controlled trial (cluster RCT).

Clusters were defined as care building or floor level within long-term care institutions.

Eligible clusters were randomized in a 1:1 ratio to either:

- Virtual Reality (VR) with Structured Debriefing Group, or
- Control Group.

Outcome assessments were conducted at three time points:

- Baseline (pre-intervention),
- End of intervention (week 3), and
- Follow-up at one month post-intervention (week 7).

4. Study Setting

The study was conducted in long-term care institutions in Taiwan. Clusters were defined as care units at the building or floor level within institutions.

All interventions and outcome assessments were implemented within participating.

5. Participants

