8.1 Primary Outcome

Empathy Level

Empathy level was measured using the full, unabbreviated Jefferson Scale of Empathy–Health Professions Version (JSE-HP), which constructs and assesses the multi-dimensional empathy levels of healthcare professionals (including perspective taking, compassionate care, and standing in patient's shoes).

The JSE-HP consists of 20 items answered on a 7-point Likert scale.

The total score ranges from a minimum of 20 to a maximum of 140. A higher total score indicates a greater level of empathy (a better outcome), whereas a lower total score represents a worse outcome.

Individual subscale scores were combined by summation to compute the final total score.

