8.2 Secondary Outcomes

Attitudes Toward Older Adults

Attitudes toward older adults were measured using the full, unabbreviated Kogan's Attitudes Toward Older People Scale (KAOP), which constructs and assesses the positive and negative sentiments toward elderly populations.

The KAOP consists of 34 items answered on a 6-point Likert scale. The total score ranges from a minimum of 34 to a maximum of 204. A higher total score indicates a more positive attitude toward older adults (a better outcome), whereas a lower total score represents a more negative attitude (a worse outcome).

Empathic behavior

Empathic behavior was measured using a Structured Empathic Behavior Rating Scale, which constructs and evaluates observable empathic behaviors exhibited by nursing assistants during direct resident caregiving interactions.

The scale utilizes a standardized checklist to rate specific behavioral interactions. The total score ranges from a minimum of 12 to a maximum of 84. A higher total score indicates a higher frequency or better quality of demonstrated empathic behaviors (a better outcome), while a lower score represents fewer or poorer empathic behaviors.

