Statistical Analysis Plan (SAP)

Title:

Effects of a Virtual Reality–Based Empathy Program on Empathy, Attitudes Toward Older Adults, and Empathic Behavior Among Nursing Assistants: A Cluster Randomized Controlled Trial

NCT No.: NCT07044492

Protocol Version: 4.0

Date: October 13, 2025

IRB Approval: Taipei Medical University Joint Institutional Review Board

IRB No.: N202203004

Principal Investigator: Principal Investigator (PI)

1. Analysis Population

All randomized participants with available outcome data were included in the analysis according to the intention-to-treat (ITT) principle.

2. Outcome Definition

The primary outcome was the empathy level score, and the secondary outcomes were attitudes toward older adults and empathic behavior; all outcomes were treated as continuous variables.

3. Descriptive Statistics

Baseline characteristics were summarized by group using:

- Mean and standard deviation for continuous variables
- Frequency and percentage for categorical variables

4. Primary Analysis

The primary analysis evaluated changes in empathy level, empathic behavior and attitudes toward older adults over time between groups using linear mixed-effects models (LMMs).

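### The only stated hypothesis concerns empathic behavior, a secondary outcome; none is stated for the primary outcome, and the SAP's primary analysis covers all three outcomes

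*Protocol*

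**What the plan says.** Protocol 2.3 states one hypothesis: the intervention group will score significantly higher than control on "empathic behavior scores over time compared with the control group". Protocol section 2 gives no other hypothesis.

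The objectives rank the outcomes differently. The primary objective (Protocol 2.1) is "To examine the effect of a virtual reality–based empathy training program on empathy level among nursing assistants". Behavior is the second of two secondary objectives (Protocol 2.2): "To assess changes in empathic behavior over time".

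The outcome sections agree with the objectives. Protocol 8.1, on the primary outcome, says "Empathy level was measured using the full, unabbreviated Jefferson Scale of Empathy–Health Professions Version (JSE-HP"; its total runs from 20 to 140. Protocol 8.2, on secondary outcomes, says "Empathic behavior was measured using a Structured Empathic Behavior Rating Scale"; its total runs from 12 to 84. SAP 2 repeats the ranking: "The primary outcome was the empathy level score, and the secondary outcomes were attitudes toward older adults and empathic behavior".

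SAP 4, headed as the primary analysis, then covers everything: "The primary analysis evaluated changes in empathy level, empathic behavior and attitudes toward older adults over time between groups". SAP 4.1 names the group × time interaction as the main parameter without tying it to one outcome. SAP 9 sets a two-sided 0.05 level for all tests. Protocol 15 says the protocol was prepared retrospectively.

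**The concern.** A reader expects the hypothesis and the primary outcome to concern the same variable. Here they do not, and no section explains the difference.

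What is at stake is which result may carry the trial's conclusion. If behavior differs between groups and the JSE-HP does not, a report could truthfully say that the study hypothesis was supported. In the reverse case it could truthfully say that the primary outcome was met. A plan fixed before the data would normally rule out one of these statements. This one was written afterwards, so it cannot serve as that safeguard unless it also discloses what was intended at the outset.

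**Working it through.** The point rests on a comparison of the text. The plan gives no figure on this matter to reproduce.

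**Step 1. Where each outcome is ranked.**

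| Place | Empathy level (JSE-HP) | Empathic behavior |
|---|---|---|
| Protocol 2.1 and 2.2, objectives | Primary | Secondary |
| Protocol 2.3, hypothesis | Not mentioned | The only hypothesis |
| Protocol 8.1 and 8.2, outcomes | Primary | Secondary |
| SAP 2, outcome definition | Primary | Secondary |
| SAP 4, primary analysis | Included | Included, with attitudes |

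Three places rank the outcomes, and all three agree. The hypothesis is the exception, and SAP 4 draws no distinction.

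**Step 2. Could the two terms mean the same thing?** No. They have different instruments and different score ranges (20 to 140 against 12 to 84), and Protocol 2 and SAP 2 list them separately. The trial could succeed on one and fail on the other. I do not rely on a contrast between self-report and observation: Protocol 8.2 describes a rating of observable behavior, but Protocol 9 says data came from questionnaires and Protocol 14 lists reliance on self-report as a limitation.

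**Step 3. Does any other section settle it?**
- SAP 4 and 4.1 apply the same model and the same main parameter to all three outcomes.
- SAP 9 gives one alpha for all tests. No section gives a testing order or an adjustment.
- Protocol 10 reports 50 + 53 = 103 participants but no power calculation, so the sample size does not reveal which outcome the trial was built around.
- The protocol carries version number 4.0, but no earlier version is included, so the sequence of decisions cannot be checked.

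**Step 4. Illustration of the error rate.** Suppose there is no true effect on any outcome, each is tested once at 0.05 from SAP 9, and any one significant result may be presented as the trial's finding. For k independent tests the chance of at least one false positive is 1 − (1 − 0.05)^k, and under any dependence it is at most k × 0.05.

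| Outcomes that could carry the claim | If independent | Upper bound |
|---|---|---|
| 1 (JSE-HP only) | 0.05 | 0.05 |
| 2 (JSE-HP and behavior) | 1 − 0.95² = 0.0975 | 0.10 |
| 3 (all in SAP 4) | 1 − 0.95³ = 0.1426 | 0.15 |

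Independence is an assumption, and a doubtful one, because the outcomes are measured on the same participants. Positive correlation would bring the figures below the middle column.

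**The case against.** The strongest reply is that the primary outcome is not in doubt. Every place that ranks outcomes names empathy level, no success rule is attached to 2.3, and the SAP never refers to the hypothesis. The documents do not call 2.3 primary or confirmatory. Any hypothesis on a secondary outcome can succeed whatever the primary outcome shows. The same model is fitted to all three outcomes in any case, so the correction changes labels and interpretation, not data or estimates.

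Much of this stands. It limits the point to an inconsistency about which result carries the conclusion. It does not remove the point: a hypothesis on a secondary outcome is harmless beside one on the primary outcome, but here it stands alone, and SAP 4 gives all three outcomes the same standing.

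Two stronger readings are tempting and are not supported:
- **That the primary outcome was switched.** The documents include no earlier version or amendment log. A drafting omission in 2.3 fits the text equally well. Retrospective preparation means that the order of events cannot be verified; it is not evidence of a switch.
- **That 2.3 itself nearly doubles the false-positive rate.** The hypothesis does not create a second primary test. The multiplicity comes from SAP 4 together with the absence of any rule in SAP 9, and the figures assume both independence and a free choice among outcomes.

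**Conclusion.** The inconsistency is real and unresolved. The sole hypothesis concerns a secondary outcome, the primary outcome has none, and the SAP's primary analysis does not single out one outcome. Because the protocol is retrospective, these documents cannot establish which outcome was confirmatory before the data were seen. Confirmatory is my term, though a lone hypothesis that predicts a significant difference invites that reading.

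The size is mainly one of interpretation: different results could be presented as the main finding. The illustrative family-wise error is about 9.8% for two outcomes and 14.3% for the three in SAP 4, under independence and free choice among them, against 5% when a single outcome carries the conclusion. The finding does not depend on these figures.

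**What to change.** Issue a dated clarification, in the protocol and the SAP, that does the following:
1. Discloses the hypothesis and the primary outcome held before the data were seen, whatever they were. The study is complete, so 2.3 should not be silently rewritten.
2. Aligns 2.3 with the JSE-HP total score, expressed through the group × time interaction already named in SAP 4.1. The SAP names no single time point for the comparison, and this correction does not need one.
3. Labels the behavior and attitude hypotheses as secondary.
4. Limits SAP 4's primary analysis to the JSE-HP and moves the other two outcomes to a secondary analysis section. Changing 2.3 alone would leave SAP 4 ambiguous.

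Base the main conclusion on the JSE-HP result. The exception is where an earlier dated version had empathic behavior as primary: then report behavior as the original primary outcome and explain the change.

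The cost is a few paragraphs across the two documents, with no new data and no change of model. The downside for the sponsor is that a positive behavior result could no longer be presented as confirming the trial's main hypothesis.

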5.1 Inclusion Criteria

Participants were eligible if they met all of the following criteria:

- Certified nursing assistants
- Aged 20 years or older
- Employed in the current institution for at least three months
- Able to communicate in Mandarin Chinese

- Provided written informed consent to participate

5.2 Exclusion Criteria

- Currently on long-term leave during the intervention period
- Severe visual, auditory, or cognitive impairment preventing participation in VR training

6. Randomization and Allocation

Clusters (care units/wards) were randomly assigned in a 1:1 ratio to either:

- Control Group (C)
- Virtual Reality (VR) with Debriefing Group

Randomization was conducted by an independent researcher not involved in recruitment or assessment.

7. Intervention

7.1 Control Group

Participants in the control group received routine education or standard practice during the study period and were provided with an empathy manual, but did not receive the VR-based empathy program.

7.2 VR With Debriefing Group

Participants in the intervention group received a virtual reality–based empathy training program designed to simulate the lived experiences of older adults in long-term care contexts. Each VR session was followed by a structured debriefing session facilitated by trained personnel, focusing on emotional reflection, perspective-taking, and application to daily caregiving practice.

The intervention was delivered over a three-week period.

8. Outcome Measures

8.1 Primary Outcome

Empathy Level

Empathy level was measured using the full, unabbreviated Jefferson Scale of Empathy–Health Professions Version (JSE-HP), which constructs and assesses the multi-dimensional empathy levels of healthcare professionals (including perspective taking, compassionate care, and standing in patient's shoes).

The JSE-HP consists of 20 items answered on a 7-point Likert scale.

The total score ranges from a minimum of 20 to a maximum of 140. A higher total score indicates a greater level of empathy (a better outcome), whereas a lower total score represents a worse outcome.

Individual subscale scores were combined by summation to compute the final total score.

8.2 Secondary Outcomes

Attitudes Toward Older Adults

Attitudes toward older adults were measured using the full, unabbreviated Kogan's Attitudes Toward Older People Scale (KAOP), which constructs and assesses the positive and negative sentiments toward elderly populations.

The KAOP consists of 34 items answered on a 6-point Likert scale. The total score ranges from a minimum of 34 to a maximum of 204. A higher total score indicates a more positive attitude toward older adults (a better outcome), whereas a lower total score represents a more negative attitude (a worse outcome).

Empathic behavior

Empathic behavior was measured using a Structured Empathic Behavior Rating Scale, which constructs and evaluates observable empathic behaviors exhibited by nursing assistants during direct resident caregiving interactions.

The scale utilizes a standardized checklist to rate specific behavioral interactions. The total score ranges from a minimum of 12 to a maximum of 84. A higher total score indicates a higher frequency or better quality of demonstrated empathic behaviors (a better outcome), while a lower score represents fewer or poorer empathic behaviors.

8.3 Timing of Assessments

All outcomes were assessed at:

- Baseline (pre-intervention),
- End of intervention (week 3), and
- Follow-up at one month post-intervention (week 7).

9. Data Collection Procedures

Data were collected using standardized questionnaires administered by trained research assistants. All assessors were blinded to group allocation where feasible.

10. Sample Size

A total of 103 nursing assistants participated in the study:

- Control Group: 50 participants
- VR with Debriefing Group: 53 participants

11. Adverse Events

The intervention was educational and non-invasive. Adverse events were monitored throughout the study period using participant self-report and

investigator observation. No adverse events were observed or reported in either study group.

12. Ethics and Informed Consent

The study was conducted in accordance with ethical principles for research involving human participants. The study protocol was reviewed and approved by the Institutional Review Board of Taipei Medical University (TMU-JIRB approval number: N202203004). All procedures were conducted in accordance with relevant ethical guidelines and regulations. Written informed consent was obtained from all participants prior to participation.

13. Data Management and Confidentiality

All data were de-identified prior to analysis. Study data were securely stored and accessed only by authorized research personnel.

14. Limitations

Limitations of the study include the limited number of participating institutions, reliance on self-reported measures, a relatively short follow-up period, and the inability to blind participants due to the nature of the intervention.

15. Protocol Status

This protocol was prepared retrospectively for results reporting purposes. All reported analyses and outcomes reflect the procedures actually implemented in the completed study.

Statistical Analysis Plan (SAP)

Title:

Effects of a Virtual Reality–Based Empathy Program on Empathy, Attitudes Toward Older Adults, and Empathic Behavior Among Nursing Assistants: A Cluster Randomized Controlled Trial

NCT No.: NCT07044492

Protocol Version: 4.0

Date: October 13, 2025

IRB Approval: Taipei Medical University Joint Institutional Review Board

IRB No.: N202203004

Principal Investigator: Principal Investigator (PI)

1. Analysis Population

All randomized participants with available outcome data were included in the analysis according to the intention-to-treat (ITT) principle.

2. Outcome Definition

The primary outcome was the empathy level score, and the secondary outcomes were attitudes toward older adults and empathic behavior; all outcomes were treated as continuous variables.

3. Descriptive Statistics

Baseline characteristics were summarized by group using:

- Mean and standard deviation for continuous variables
- Frequency and percentage for categorical variables

4. Primary Analysis

The primary analysis evaluated changes in empathy level, empathic behavior and attitudes toward older adults over time between groups using linear mixed-effects models (LMMs).

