4.1 Model Specification

- Fixed effects: group, time, group \times time interaction
- Random effects: cluster (care unit/ward) and participant
- Covariance structure: unstructured

The primary parameter of interest was the group \times time interaction term.

5. Handling of Clustered Data

Clustering at the care unit/ward level was accounted for through random effects in the mixed-effects models.

6. Handling of Missing Data

Missing outcome data were handled using multiple imputation (MI) under the missing-at-random (MAR) assumption.

Mixed-effects models were estimated using maximum likelihood methods, allowing inclusion of participants with incomplete outcome data.

7. Sensitivity Analyses

Sensitivity analyses were conducted to assess the robustness of findings under alternative missing data assumptions.

8. Statistical Software

All analyses were performed using IBM SPSS Statistics version 25.0 (IBM Corp., Armonk, NY, USA).

9. Statistical Significance

All statistical tests were two-tailed with a significance level of $\alpha = 0.05$.

10. Deviations from the Protocol

Any deviations from the pre-specified analysis plan were documented and justified prior to data analysis.

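### The 5% error rate is not assured for the trial's claim, because the documents disagree on which outcome carries it and fix no deciding interaction test

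*SAP*

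**What the plan says.** Three places bear on which outcome carries the claim, and they do not agree.

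- SAP 2 ranks the outcomes: "The primary outcome was the empathy level score, and the secondary outcomes were attitudes toward older adults and empathic behavior". Protocol 2.1 and 8.1 agree that empathy level, measured by the JSE-HP, is primary.
- SAP 4, under the heading for the primary analysis, does not rank them: "The primary analysis evaluated changes in empathy level, empathic behavior and attitudes toward older adults over time between groups", all by linear mixed model.
- Protocol 2.3 gives the trial's only hypothesis: the intervention arm will have significantly higher "empathic behavior scores over time compared with the control group".

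On the test itself, SAP 4.1 makes the group-by-time interaction the primary parameter. It does not say whether time is categorical or linear, whether the term is tested jointly or visit by visit, or which visit decides. Protocol 3 says "Outcome assessments were conducted at three time points": baseline, week 3 and week 7. SAP 9 adds: "All statistical tests were two-tailed with a significance level of" 0.05. Neither document gives a multiplicity adjustment, a testing order or a success rule.

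**The concern.** A reader needs to know which single result decides whether the program worked. SAP 2 points to the JSE-HP, SAP 4 to any of three outcomes, and Protocol 2.3 to empathic behavior. With each test at 0.05, a significant result on a secondary outcome could be presented as part of the primary analysis or as confirming the stated hypothesis, and nothing in the plan would contradict that.

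The interaction is a second gap. If time is categorical, three visits give two change-from-baseline contrasts per outcome. A joint 2-df test does not by itself say at which visit the arms differ, and two contrasts read separately give two chances of success. At stake is the false-positive rate behind the headline result, and whether the report can emphasise one outcome or visit selectively.

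**Working it through.** **Inputs.** From the documents: two-tailed alpha 0.05 for every test (SAP 9); three outcomes in the primary analysis (SAP 4); one named primary outcome (SAP 2, Protocol 8.1); three visits (Protocol 3 and 8.3), hence 3 − 1 = 2 interaction contrasts per outcome if time is categorical and 1 if it is linear. Assumed, because the documents give none: correlation between outcomes of 0 to 0.7, and correlation of 0.5 between the week 3 and week 7 contrasts of one outcome. The latter is positive because both contrasts share a baseline.

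**Step 1: the plan's own figure.** One outcome and one test: 1 − 0.95¹ = 0.050. This matches SAP 9. A joint 2-df test of the JSE-HP interaction is also one test; simulated under the null, it rejects 5.0% of the time.

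**Step 2: three outcomes, one interaction test each.** Under independence, 1 − 0.95³ = 1 − 0.8574 = 0.143. The upper bound is 3 × 0.05 = 0.15.

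**Step 3: two contrasts per outcome, read separately.** For a single outcome, 1 − 0.95² = 0.0975 under independence, and about 9.1% by simulation at a between-visit correlation of 0.5. For three outcomes there are 3 × 2 = 6 contrasts, with an upper bound of 6 × 0.05 = 0.30.

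**Step 4: correlated tests.** Simulated from multivariate normal statistics under the global null, with correlation 0.5 between visits:

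| Correlation between outcomes | Any of three joint tests | Any of six contrasts |
|---|---|---|
| 0 | 14.3% | 24.8% |
| 0.3 | 13.7% | 23.8% |
| 0.5 | 12.7% | 22% |
| 0.7 | 11.1% | 19% |

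Three single-contrast tests (for example one linear slope per outcome) give nearly the same as the joint tests: about 13.6%, 12.6% and 10.9% at 0.3, 0.5 and 0.7.

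**Step 5: what a joint test costs in power.** Take a contrast with 80% power as a 1-df test, so non-centrality (1.96 + 0.84)² = 7.84. If the other contrast adds no information, the 2-df test has the same non-centrality and 71% power. If the effect is equal at both visits, the non-centrality is 2 × 7.84 / (1 + ρ): 10.45 at ρ = 0.5 and 9.22 at ρ = 0.7, giving 83% and 78%. The direction of the change therefore depends on the pattern of effect.

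All of this is large-sample theory. The number of clusters is not stated, so small-cluster effects are left out.

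**The case against.** The strongest reply is that SAP 2, Protocol 2.1 and Protocol 8.1 all name one primary outcome, and that SAP 4 merely says the same model was fitted to every outcome under a loose heading. On that reading, a JSE-HP claim judged by one joint interaction test holds 5%. This stands, and it is why the conclusion is that 5% is not assured. It does not remove the conflict: the benign reading follows SAP 2 over SAP 4, sets aside Protocol 2.3, and supplies a joint-test rule that SAP 4.1 never states.

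A reader might infer several stronger things that the documents do not support.

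- *That the 5% rate fails outright, or that the plan has six primary tests.* The ranking in both documents speaks against this, and two contrasts per outcome require categorical time, which is not stated. A joint test and two separate contrasts are also alternatives; the plan cannot be charged with the drawbacks of both.
- *That the family-wise error is 1 − 0.95⁶ = 26.5%.* This treats contrasts that share a baseline as independent.
- *That a joint test necessarily cuts power from 80% to 71%.* That is the case where the second contrast adds nothing; Step 5 shows 78% or 83% with equal effects at both visits.
- *That a joint test is unusable because it could be significant for an adverse pattern.* A two-tailed single contrast can be too; direction is read from the estimates.
- *That week 7 is the intended deciding visit.* Protocol 1 remarks that conventional training may have limited sustained impact, but states no aim that selects a visit. Week 3 and week 7 are listed equally.

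**Conclusion.** The plan is wrong as written on this point. SAP 4 and Protocol 2.3 conflict with the single primary outcome in SAP 2 and Protocol 8.1, and no rule says which result decides.

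The size depends on how success is declared. For JSE-HP alone with one joint test, the error rate is 5%. For any of three outcomes with one test each, it is 14.3% if independent and about 11–14% at between-outcome correlations of 0.3–0.7. For any of six separate contrasts with categorical time, it is about 19–25% at a between-visit correlation of 0.5 and between-outcome correlations of 0–0.7. The correlations are assumptions. The documents do not settle which case applies, and that is the defect.

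Protocol 15 limits the remedy. The protocol was prepared after the study was completed, so a rule written now clarifies the report but cannot restore pre-specified error control.

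**What to change.** 1. Limit the primary analysis in SAP 4 to JSE-HP, and align the hypothesis in Protocol 2.3 with it.
2. In SAP 4.1, state that time is categorical and that the JSE-HP group-by-time interaction is judged by one joint test. One named change-from-baseline contrast is an acceptable alternative if records that predate the results support the choice of visit; otherwise label that choice post hoc. Word it as a difference in change from baseline: a plain between-arm difference at a visit is not the interaction contrast unless baseline means are constrained equal.
3. Report attitudes and empathic behavior as secondary, either Holm-adjusted (smaller p-value against 0.05/2 = 0.025, then the other against 0.05) or labelled as not adjusted for multiplicity.
4. Show all six contrasts with confidence intervals, which guards against selective emphasis whichever test decides.
5. State that any hierarchy added now is post hoc, given Protocol 15.

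The cost is rewording in both documents and a relabelled results table; no new data are needed. The downside is that a significant secondary result can no longer be presented as the primary finding, and some secondary p-values become less favourable.
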